### Study Timeline:

After informed consent the QST profile (NASQ in the figure) will be performed as seen in Figure xx. Follow-up QST testing as described above will only be performed in subjects who undergo endoscopic therapy or surgery.

Figure 4: Study timeline

### Experimental endpoints (quantitative sensory testing - QST)

*Repetitive pinprick stimulation (temporal summation):* Recording of temporal summation to repetitive pinprick stimulations in the pancreatic and control area (midline volar site of dominant forearm) will be employed using a 8mN PinPrick device (Pin-Prick Stimulatoren, MRC Systems GmbH, Heidelberg, Germany). Pain ratings using a 0-10 NRS scale will be obtained after a single application, and after the last application in a series of ten repetitive stimuli with an inter-stimulus interval of 1 second. For accurate timing of the stimuli the procedure is guided by an auditory signal using a metronome. The difference between the last and the first scores of the ten stimuli will be recorded as the temporal summation score.

*Muscle pressure stimulation:* The pressure pain detection threshold (PDT) and pain tolerance threshold (PTT) will be determined for the following skin dermatomes: C5 (clavicula), T10 ventral (upper epigastric area – pancreatic viscerotome), T10 back (pancreatic viscerotome), L1 (anterior superior iliac crest) and L4 (the quadriceps 15 cm above the patella). All lateralized pressure stimulations are applied on the subject's dominant side. An electronic pressure algometer (Algometer Type II, SBMEDIC Electronics, Solna, Sweden) with a probe surface area of 1 cm^2 is used for the pressure stimulations. Pressure will be increased in two sessions at a rate of 30 kPa per second until the PDT or PTT is reached and subjects will be instructed to press a button at this point. The assessment parameter is the pressure at the predefined sensory threshold measured in kPa.

*Bone pressure stimulation:* The same pressure algometer as described above will be used to mechanical stimulation on the right tibia bone, but with a specially designed probe of 3.1 mm^2 (Aalborg University, Denmark). The device has been used in previous studies and proven its reliability and validity. Pressure will be applied at the tibial bone on the dominant site 10 cm distal to the lowest border of patella with a pressure rate at 30 kPa per second. Pain thresholds are determined as for muscle pain.

*Cold pressor test:* The dominant hand is immersed in an ice-chilled water bucket (2.0°C ± 0.3°C). The subject will be told to remove the hand from the water after 2 minutes of immersion or sooner if the pain is intolerable. The subjects rate the pain intensity for every 10 seconds during the cold pressor test using a 0-10 NRS rating scale. If the subject withdraws their hand sooner than two minutes, due to intolerable pain, the VAS will be considered to be 10 for the remaining period of time and the time for withdrawal of the hand will be noted.

*Conditioned pain modulation (CPM):* CPM is a clinically measurable form of descending pain modulation that can be induced experimentally by a conditioning stimulus (the cold pressor test) and quantified by applying a “test-pain” (pressure stimulation on the non-dominant quadriceps musculature 4 cm above the patella) before and after the conditioning stimulus. The difference in pressure stimulus intensity (PTT) before and after the cold pressor test provides a quantitative index of the CPM capacity in the individual subject. The techniques used for pressure stimulation and cold pressor test described above will be combined to measure CPM.

QST testing will be performed at the GI clinic or Digestive Disorders Center or the GI lab at UPMC-Presbyterian and UPMC-Shadyside Hospital by the clinical research coordinator or a physician investigator.

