**Title: Predicting treatment response in Chronic Pancreatitis using Quantitative Sensory Testing**

**Date: January 3, 2018**

## Predicting treatment response in Chronic Pancreatitis using Quantitative Sensory Testing

### Objective:

Endoscopic therapy or surgery for treatment of pain is typically offered to chronic pancreatitis (CP) patients with pancreatic ductal strictures and/or stones. However, clinical pain symptoms correlate poorly with pancreatic ductal morphology, response to endoscopic or surgical therapy is unpredictable, and the rationale for invasive therapies is often questioned.

Quantitative sensory testing (QST) can map the pain system; the technique is based on the rationale that different neural pathways and networks can be explored using standardized stimulation and simultaneous recording of the evoked pain response by psychophysical and/or objective methods. We hypothesize that endoscopic or decompressive surgical therapy is most effective for patients with local sensitization without systemic or abnormal activation of the central pain system. Our objective is to distinguish phenotypes characterized by segmental sensitization of the pancreatic viscerotome (T10), and systemic sensitization with pathological central pain processing including augmented temporal summation and impaired descending pain inhibition.

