### Aims:

- Aim 1) Investigate the association between QST profiles and demographic and clinical characteristics including depression and anxiety questionnaires in patients with suspected or definite CP.
- Aim 2) Investigate if the QST profile of the individual patient can be used to predict the clinical outcome of endoscopic or surgical treatment in patients with suspected or definite CP.
- Aim 3) Investigate the temporal evolution and association of QST profiles and clinical pain scores after endoscopic or surgical treatment in patients with suspected or definite CP.

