systematically. After surgery, it has been shown that the initial changes in pain processing (using the NASQ) in the days after surgery can predict who will develop chronic postsurgical pain (Wilder-Smith 2015). For example, we recently showed that early postoperative hyperalgesia to pressure stimulation in the first days after surgery was an independent risk factor for development of chronic pain (van Helmond et al. In preparation 2016).

In CP, we have used NASQ to detect differences in generalised sensitization (overall difference between the blue and green curves in figure 1) as well as changes in the sensation between different dermatomes (for example the hyperalgesia at T10 in figure 1) together with assessment of CPM. Hence, we have showed that patient with increased sympathetic drive have increased pain to QST in general (Buscher et al. 2010), and the degree of generalised sensitization correspond with the MANNHEIM severity index (the more diseased, the more pain) as well as response to splanchnicectomy (Bouwense et al. 2011; Bouwense et al. 2013). The methods have also been used to guide treatment, as selective sensitization at the pancreatic dermatome (T10) rather than generalized sensitization was shown to predict the effect of pregabalin (Olesen et al. 2013). We have also shown that patients with CP suffer from deficient descending inhibition as reflected in CPM. Drugs such as tapentadol and venlafaxine may potentiate this mechanism in patients with neuropathy (Yarnitski et al. 2012; Niesters et al. 2015). We therefore believe that these drugs are helpful in many patients with pain due to pancreatitis, where a large fraction is thought to have neuropathic pain (Drewes et al. 2008).

Notably, QST profiles from CP patients have been reported only in Europeans to date: no data exist at this time on CP patients in the United States.

[figure not shown]
*Figure 1. The different dermatomes tested (left) and a profiling of controls and patients with different degree of sensitization to pressure pain stimulation (right)*

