**Followup Testing:**

As part of their regular medical care, some subjects may undergo Endoscopic Ultrasound (EUS), Endoscopic Retrograde Cholangiopancreatography (ERCP), Extracorporeal Shock Wave Lithotripsy (ESWL), surgery, laboratory and imaging studies, and medical treatment. We will review medical records to collect data on these variables prior to enrolment and during the course of the study.

Follow-up testing will be limited to subjects who undergo endoscopic treatment or surgery for the pancreatitis or for SOD. These subjects will fill out a pain diary for 7 days prior to their intervention, as well as for seven days before each follow-up research visit at 1 month, 3 month, and 6 months post-intervention. The pain diary is designed to assess pain intensity and dynamics over time, and is based on a 0-10 NRS rating scale. Both the median and maximal pain for the last 24 hours is registered. It will take approximately 5 minutes per day for subjects to complete the pain diary. These subjects will also undergo QST testing at each follow-up visit at 1 month, 3 months, and 6 months. Lastly, these subjects will fill out the same baseline questionnaires (PROMIS, EORTC-QLQ-C30, mBPI-sf, HADS, PCS), and additionally the Patient’s Global Impression of Change (PGIC) questionnaire for assessment of change in symptoms over time.

**Study Timeline:** Study procedures at baseline and during follow-up and which groups of study subjects will complete individual procedures

	Baseline	Follow-up day 30 post- intervention	Follow-up day 90 post- intervention	Follow-up day 180 post- intervention
QST Testing	All Subjects	Subjects who underwent invasive intervention	Subjects who underwent Invasive intervention	Subjects who underwent invasive intervention
Standardized Patient Questionnaires (PROMIS, EORTC, HADS, BPIsf, PCS)	All Subjects	Subjects who underwent invasive intervention (Add PGIC)	Subjects who underwent invasive intervention (Add PGIC)	Subjects who underwent invasive intervention (Add PGIC)
Pain Diary for 7 days prior		Subjects who underwent invasive intervention	Subjects who underwent invasive intervention	Subjects who underwent invasive intervention
Personal medical history	All Subjects	Collect changes from subjects who	Collect changes from subjects who	Collect changes from subjects who

[figure not shown]
		underwent invasive intervention	underwent invasive intervention	underwent invasive intervention

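### In surgically treated subjects, follow-up ventral T10 thresholds may carry a local wound effect that Aim 3 cannot tell apart from pancreatic-viscerotome sensitization

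*Protocol*

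**What the plan says.** The Objective section makes "segmental sensitization of the pancreatic viscerotome (T10" one of the two phenotypes the study sets out to distinguish, the other being systemic sensitization. The QST section names two pressure sites for that viscerotome, the first of them "T10 ventral (upper epigastric area"; the full listing reads "T10 ventral (upper epigastric area – pancreatic viscerotome), T10 back (pancreatic viscerotome". It also specifies "repetitive pinprick stimulations in the pancreatic and control area (midline volar site of dominant forearm", without saying whether the pancreatic area is on the abdomen or the back. The Device section repeats both descriptions.

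Under Followup Testing, "Follow-up testing will be limited to subjects who undergo endoscopic treatment or surgery for the pancreatitis or for SOD", and "These subjects will also undergo QST testing at each follow-up visit at 1 month, 3 months, and 6 months". The timeline table footnote defines the intervention as either endoscopic therapy or surgery. No section gives operated subjects a different test site, a distance from a scar, or a record of where the incision lies.

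Aim 3 is to "Investigate the temporal evolution and association of QST profiles and clinical pain scores after endoscopic or surgical treatment". The statistical methods paragraph assigns change over time to mixed models and mentions no distinction by type of intervention. The Background reports that "early postoperative hyperalgesia to pressure stimulation in the first days after surgery was an independent risk factor for development of chronic pain".

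**The concern.** A threshold measured over the upper epigastrium before an operation and again afterwards may not measure the same thing both times. Before treatment, a low ventral T10 threshold is meant to reflect visceral input from the pancreas. After an abdominal operation, the same reading can also reflect a healing incision, a scar or an injured skin nerve. The plan labels the reading pancreatic viscerotome in both cases.

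What is at stake is Aim 3: the course of the segmental T10 component after treatment, its association with clinical pain, and any comparison of that course between surgical and endoscopic subjects. If the wound effect cannot be separated at the visit, later modelling can recover it only in part, because scar position relative to the probe would not have been captured.

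**Working it through.** The protocol states no figure to reproduce: it has no power calculation, effect size or standard deviation for QST change. The check is a comparison of sections, followed by a simple expression for the bias.

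**Step 1: is the same site tested before and after surgery?** Yes. The QST section fixes ventral T10 in the upper epigastrium. Followup Testing and the timeline repeat QST at 1, 3 and 6 months in everyone who had endoscopic treatment or surgery, with no change of site.

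**Step 2: would a local effect look like the phenotype of interest?** Segmental sensitization means a lower threshold at T10 than at remote sites.

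| Cause of change | Ventral T10 | T10 back | C5, L4, tibia |
|---|---|---|---|
| Segmental pancreatic sensitization | shifts | shifts | little change |
| Local wound effect | shifts | little change, unless surgery has a segmental effect | little change |

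The remote sites do not separate the two causes. T10 back does so in part, and it is already tested at every visit, but the protocol does not say it should be preferred after surgery.

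**Step 3: direction.** Wound hyperalgesia would lower the threshold and look like persisting or worsening sensitization. Nerve injury could raise it and look like relief. The sign is therefore not fixed. For pinprick, the score is the last rating minus the first, so a local effect that raises both ratings equally cancels. Only an effect on the increment matters, and only if the pancreatic area is on the abdomen.

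**Step 4: size.** Let s be the surgical share of treated subjects and w the mean local shift at ventral T10 among them.

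- Bias in the pooled mean change: s × w
- Bias within the surgical subset: w
- Bias in a surgical-minus-endoscopic contrast: w − 0 = w

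Neither s nor w can be taken from the documents. The sample size paragraph gives a minimum of 60 subjects for endotherapy and no number for surgery. Purely as assumptions, take s from 10% to 30% and |w| from 20% to 30% of the threshold:

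- Low end: 0.10 × 20% = 2% pooled
- High end: 0.30 × 30% = 9% pooled
- Surgical subset and contrast: the full 20% to 30%

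If s = 0 the pooled bias is zero. These values show how the expression behaves; they are not estimates for this trial.

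**Step 5: what is outside its reach?** Aim 1 and the predictors in Aim 2 use baseline QST, taken before the intervention in subjects without prior pancreatic surgery. The primary endpoint compares QST profiles across diagnostic groups and controls, and untreated subjects have only a baseline test. The secondary endpoint is the day-90 change in diary pain. None of these uses post-operative ventral T10, and endoscopic subjects have w = 0.

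**The case against.** The strongest case against is that the protocol nowhere gives the operation, approach or incision site. A reader might infer that the ventral site lies in the operative field. That is plausible for pancreatic surgery, but it is not in the text. A reader might also infer that the pinprick is abdominal. The text says only the pancreatic area, and T10 back carries the same viscerotome label, so the pinprick may be dorsal. Both objections stand, and the point is worded accordingly.

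A reader might take the Background as proof that wound hyperalgesia will be recorded as sensitization. It does not go that far. The hyperalgesia it cites was seen in the first days after surgery, the test site relative to the wound is not given, and the first follow-up here is at 1 month. It shows that the authors expect surgery to alter pressure-pain processing; it does not show an artefact at 1, 3 or 6 months. Nor do the documents support a bias that always runs against treatment benefit, for the reason given in Step 3. The exclusion of prior pancreatic surgery is no evidence that the authors recognised this problem, since its reason is not stated.

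It is also fair that Aim 3 concerns a multi-site profile, that nothing says ventral T10 will be read alone, that this is an exploratory pilot, and that covariates in a mixed model are commonly left to an analysis plan that is not shown. Data on surgery and endoscopy are already collected from records, so intervention type is available for modelling. These points limit the reach but do not remove the concern. The test site and its label are fixed in the protocol, and scar position must be recorded at the visit or it is lost.

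**Conclusion.** The concern holds in a limited form. In surgically treated subjects, follow-up pressure thresholds at ventral T10 may be shifted by a local wound, scar or nerve effect in either direction, and so may pinprick summation if tested on the abdomen. Followed as written, Aim 3 could read that shift as a change in pancreatic-viscerotome sensitization, and surgical and endoscopic courses would not be comparable on this measure.

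The size cannot be stated. It is s × w in a pooled analysis and w within the surgical subset, with both quantities absent from the documents. The conclusion assumes that at least some treated subjects have surgery and that at least some incisions lie near the ventral site. It does not extend to baseline QST, endoscopic subjects or the two named endpoints. It is worth correcting because the correction is cheap, not because the trial's main results depend on it.

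**What to change.** Amend three places.

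- **Followup Testing:** at each post-surgical visit, record the position of any abdominal scar relative to the ventral T10 test site.
- **Experimental endpoints (QST):** state that after surgery the main viscerotome measure for Aim 3 is T10 back. State whether the pancreatic area for pinprick is ventral or dorsal. Report post-operative ventral T10 (and abdominal pinprick, if used) separately, and do not interpret them as evidence of pancreatic sensitization.
- **Statistical methods:** model QST change by intervention type, endoscopic versus surgical.

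Baseline testing stays as it is for everyone, and no new test is added. The cost is less usable ventral follow-up information in the surgical subset, plus one extra recorded item per visit. T10 back is not a perfect substitute, because it may share some segmental effect of the surgery; this should be acknowledged when surgical courses are reported.

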#### **Device:**

Recording of temporal summation to repetitive pinprick stimulations in the pancreatic and control area (midline volar site of dominant forearm) will be employed using a 256 nm Von Frey Hair (Pin-Prick Stimulatoren, MRC Systems GmbH, Heidelberg, Germany).

The pressure pain detection threshold (PDT) and pain tolerance threshold (PTT) will be determined for the following skin dermatomes: C5 (clavicular), T10 ventral (upper epigastric area – pancreatic viscerotome), T10 back (pancreatic viscerotome), L1 (anterior superior iliac crest) and L4 (the quadriceps 15 cm above the patella), with an electronic pressure algometer (Algometer Type II, SBMEDIC Electronics, Solna, Sweden) with a probe surface area of 1 cm^2 is used for the pressure stimulations. Bone pressure stimulation will be measured with a probe of 3.1 mm^2 (Aalborg University, Denmark). The device has been used in previous studies and proven its reliability and validity.

#### **Questionnaires to be used in the study:**

Hospital Anxiety and Depression Scale (HADS)

PROMIS Global Health Scale (PGHS)

Modified Brief Pain Inventory – short form (mBPI-sf)

Pain Catastrophizing Scale (PCS)

European Organisation for Research and Treatment of Cancer Quality of Life Questionnaire (EORTC-QLQ-C30)

Patient's Global Impression of Change (PGIC)

#### **Clinical Outcomes:**

The primary clinical endpoint will be:

- QST profile of subjects with Definite or Suspected CP, SOD, Functional Dyspepsia, and controls

The secondary clinical endpoint will be:

- In subjects undergoing endoscopic or surgical treatment - The absolute and percentage change from baseline in ratings of average pain in the past week at day 90 using a daily pain diary based on a 0-10 numerical rating scale (NRS). A percentage change of  $\geq 30\%$  is considered clinically significant.

### **Sample Size:**

#### **Sample size determination and statistical methods**

This is an explorative pilot study and therefore no formal power calculation has been conducted.

We plan to enroll a total of 500 subjects in the study, of whom at least 60 will be undergoing endotherapy, and at least 100 will be controls. The analysis of clinical and experimental endpoints will be by per-protocol, meaning that only subjects completing the experimental setup are included. The predictive value of the QST profiles will be analyzed using logistic regression and machine learning. Mixed models will be used to analyze the changes in clinical and experimental endpoints over time and subsequent analyses directed at the secondary clinical and experimental endpoints are analyzed using appropriate statistics.

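### Aim 2 prediction is assigned to logistic regression with no outcome named, and no model of the continuous diary score is tied to QST prediction

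*Protocol*

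**What the plan says.** Aim 2 asks whether an individual patient's QST profile predicts the clinical outcome of endoscopic or surgical treatment. The Protocol section Sample size determination and statistical methods gives the method: "The predictive value of the QST profiles will be analyzed using logistic regression and machine learning". No dependent variable is named there.

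Under Clinical Outcomes, the secondary endpoint applies "In subjects undergoing endoscopic or surgical treatment" and is "The absolute and percentage change from baseline in ratings of average pain in the past week at day 90 using a daily pain diary", on a 0-10 numerical rating scale. A percentage change of at least 30% "is considered clinically significant". The protocol gives no other cut for a treatment outcome.

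Mixed models are planned for changes in clinical and experimental endpoints over time, and unspecified suitable methods for the secondary endpoints. Neither is described as the QST prediction analysis.

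On numbers, the protocol plans 500 subjects, "of whom at least 60 will be undergoing endotherapy". Analysis is per protocol, "meaning that only subjects completing the experimental setup are included". On power: "This is an explorative pilot study and therefore no formal power calculation has been conducted".

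**The concern.** Naming logistic regression means the outcome must be categorical, while the endpoint is a change on a numerical scale. If the outcome is the 30% cut, a patient who improves by 29% is coded the same as one who worsens, and a patient who improves by 31% the same as one who becomes pain-free. The question in the title is answered only in the treated patients, a small part of the 500. A less efficient outcome there gives wider intervals and makes it easier to conclude wrongly that QST does not predict response.

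There is a second, smaller reason to doubt a percentage cut as the lead outcome. The inclusion criteria for definite CP and for SOD set no minimum pain intensity, whereas suspected CP requires a score above 3. For a treated patient whose baseline diary pain is 1, a 30% change is 0.3 points; at 0 it is undefined. How many treated patients start that low is not known.

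**Working it through.** **Plan's own figure.** None to reproduce: the protocol states no power, alpha or effect size, and no derivation of 500, 60 or 100.

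**Inputs.** From the protocol: model type, continuous 0-10 diary outcome, 30% cut, and a minimum of 60 endotherapy patients. Assumed because the protocol gives no values: responder rate p from 20% to 80%, QST-pain correlation r from 0.30 to 0.40, two-sided alpha 0.05, and normal outcomes linear in QST.

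**Step 1: information kept by a yes/no outcome.** For a normal outcome cut so that a proportion p respond, the asymptotic relative efficiency is φ(z_p)² / [p(1 − p)]. At p = 0.5: 0.3989² / 0.25 = 0.637. At p = 0.3: 0.3477² / 0.21 = 0.576.

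| Responder rate | Efficiency | Loss | 60 patients are worth | Needed to match 60 |
|---|---|---|---|---|
| 50% | 0.637 | 36% | 38 | 94 |
| 40% or 60% | 0.622 | 38% | 37 | 96 |
| 30% or 70% | 0.576 | 42% | 35 | 104 |
| 20% or 80% | 0.490 | 51% | 29 | 122 |

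The last two columns are 60 × efficiency and 60 ÷ efficiency. The proportional loss does not depend on n.

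**Step 2: power at n = 60, single predictor.** The Fisher z approximation for the continuous outcome is Φ(atanh(r)·√57 − 1.96). At r = 0.30: 0.3095 × 7.550 − 1.96 = 0.377, so power is 65%. At r = 0.35 it is 79%, and at r = 0.40 it is 89%. Simulation with 1,500 runs per cell, at responder rates of 30%, 50% and 60%, gave:

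| r | Linear regression | Logistic regression | Gap within the same cell |
|---|---|---|---|
| 0.30 | 66-67% | 47-48% | 18-20 points |
| 0.35 | 77-81% | 59-60% | 18-22 points |
| 0.40 | 90-91% | 68-74% | 16-23 points |

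**Step 3: both models adjusted for baseline pain.** A separate simulation at n = 60 with standardised QST effects of 0.30, 0.35 and 0.40 gave 71-75% against 49-54%, 86-87% against 67-70%, and 93-94% against 75-79%. Taking midpoints, the gaps are 73 − 51.5 = 21.5, 86.5 − 68.5 = 18 and 93.5 − 77 = 16.5 points. Steps 2 and 3 together support roughly 15 to 23 points.

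**Step 4: does it survive a different response pattern?** Assume instead two distinct groups: half respond, QST raises the log-odds of responding by 0.8 per SD, responders improve by 60-70%, non-responders by 0%, with an SD of 15-25 percentage points. Power in three such settings was 68%, 63% and 56% for the continuous model, against 77%, 72% and 58% for the responder model. The responder model was ahead by 9, 9 and 2 points. The loss in Steps 1 to 3 is therefore conditional on the linear, normal model.

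**Step 5: sample size.** The 60 is a minimum for endotherapy only. Surgical patients add to it and the completer rule subtracts. If 10% to 20% failed to complete (assumed), 60 would become 60 × 0.9 = 54 or 60 × 0.8 = 48 before surgical patients are added. The analysed number is unknown in both directions.

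**The case against.** A fair defence has five parts.

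- **The outcome is not stated.** A reader might infer that the protocol fixes the 30% cut as the logistic outcome. It does not: it only calls that change clinically significant. The Patient's Global Impression of Change is also collected after intervention and could supply a response outcome, although no cut is set for it. Naming the outcome may also be left to an analysis plan that is not shown. This stands, so the cut is the likely outcome, not the stated one. The choice of logistic regression, however, is made in the protocol itself.
- **Other analyses are planned.** Machine learning could use the continuous change, and the mixed models analyse pain over time. Aim 3 also looks at QST and pain scores together after treatment. This stands in part: none of these is specified as a continuous-outcome model for QST prediction.
- **A responder model suits the aim.** The hypothesis is about distinct phenotypes, and the Background asks for individual responders to be identified. This stands, and is the reason to keep the logistic model.
- **The loss depends on the model.** Step 4 shows this. A reader might infer that about a third of the information is discarded whatever the truth; that does not follow.
- **It is a pilot.** No power is claimed and pain change is a secondary endpoint. This lowers the severity.

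**Conclusion.** The point holds as a modest improvement. The protocol commits QST prediction to logistic regression and machine learning, leaves the dependent variable unnamed, and ties no continuous-outcome model to it although the diary supplies a continuous score. Under a linear relation with normal noise, a yes/no outcome costs 36% of the information at a 50% responder rate and 42% at 30% or 70%, or roughly 15 to 23 points of power at n = 60. Under a sharply bimodal response the cost can disappear or change sign. Responder rate, effect size and the shape of the response are all assumptions, since the protocol gives none of them.

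Nor should the treated sample be read as about 60: the text says "at least 60 will be undergoing endotherapy", which leaves out surgical patients and does not allow for non-completers. Nothing here contradicts a stated power figure, because there is none.

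**What to change.** For Aim 2, make the lead analysis a linear model of the day-90 weekly diary mean on the QST measures, adjusted for baseline diary pain from the seven days before intervention. The QST-by-visit term at day 90 in the mixed model already planned would serve equally. Name the 30% response at day 90 as the outcome of the logistic model, and keep that model as the supportive, individual-responder analysis. State which outcome the machine learning will use.

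The cost is a few sentences of protocol or analysis-plan wording, with no new data, visits or patients. The one drawback is that the lead effect is expressed in rating-scale points; the odds ratio for response is still reported beside it. If response proves to be bimodal, the retained logistic model covers that case.
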